8.3 Selection criteria of surgeons

In order to strictly guarantee the homogeneity of the surgeons, they need to meet a certain standard. Generally, they are required to have more than 5 years of endoscopic surgery experience and more than 1 year of robotic surgery experience, and have passed the test product training and obtained the operation training certification.

9. Safety evaluation

9.1 Safety evaluation indicators:

- (1) The incidence of organ and vascular injury events which include the following:
 - 1) Any damage to the adjacent organs (liver, spleen and intestine) due to the malfunction of the products.
 - 2) The blood vessel injury caused by the malfunction of the products during the operation resulting in massive bleeding.
- (2) The incidence of adverse events from the end of the operation to discharge.
- (3) The incidence of the malfunction of the products which includes the following:
 - 1) The connection between the console and the operative arms receives strong interference, which cannot be solved by resetting.
 - 2) The tissue cannot be loosened when the surgical instrument is clamped.
 - 3) Device installation false alarm.
 - 4) Failure or damage of the surgical instruments during an operation.
- (4) Vital signs: temperature, heart rate, respiration, and mean arterial pressure.
- (5) Laboratory examinations: blood routine, liver and kidney function, and electrolytes.

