Clinical Trial Protocol

TITLE: Prospective, Multicenter, Randomized, Single-blind, Parallel-controlled Clinical Trial Protocol for the Safety and Efficacy of Clinical Applications of the Endoscopic Instrument Control System

PROTOCOL ID: SDWG-NST600S-CT

DOCUMENT TYPE: Study protocol

DATE: 2019-09-01

SPONSOR: The Third Xiangya Hospital of Central South University

COLLABORATOR: The Affiliated Hospital of Qingdao University

Study protocol

1. Study purpose

To evaluate the safety and efficacy of the MicroHand S endoscopic instrument control system by using it in clinical treatment for the participants. Statistical analysis is conducted to determine whether the efficacy of the test product is non-inferior to that of the control product and to observe the incidence of organ and vascular injury related to the test product. Thus, to verify the safety and efficacy of the MicroHand S endoscopic instrument control system developed by WEGO Surgical Robot Co., Ltd in clinical application.

2. Content

This clinical trial is a prospective, multicenter, randomized, single-blind, parallel-controlled study. The instrument used in the experimental group is the endoscopic surgical robotic system developed by WEGO Surgical Robot Co., Ltd., and the instrument used in the control group is the endoscopic surgical robotic system developed by Intuitive Surgical.

Before patients are enrolled in this clinical study, the researchers will do a detailed screening of the subjects based on the inclusion and exclusion criteria to determine if the patients are appropriate for the clinical study. Patients who meet the conditions of the study will be required to sign an informed consent form. Then they will be randomly assigned to the test group or the control group. The surgical robot system will be used for treatment in both groups to evaluate the primary and secondary outcome measures and to observe the incidence of organ and vascular injury.

Finally, we evaluate the safety and efficacy of the test product through the comparison of the data obtained from the test group and the control group during the treatment.

3. Background

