5. Study Methods

- (1) This study uses a multicenter, randomized, single-blind, parallel-controlled method to observe the efficacy and safety of the MicroHand S endoscopic instrument control system in clinical application.
- (2) The subjects' vital signs are recorded before the start of this study, which include blood routine, liver and kidney function, electrolytes, coagulation function, electrocardiogram, urine/blood pregnancy test (female) and related imaging examination. Preoperative combined medications are also recorded.
- (3) Qualified subjects are divided into the experimental group and the control group by randomized number given in an envelope. Both the endoscopic instrument control systems in two groups are examined before the test. After anesthesia, the endoscopic instrument control system is placed in an appropriate position. Then we connect the wires and power up the system. According to the requirements of the surgery, the operative arms are placed and slowly pushed through the Trocars of the abdominal wall. The surgeons start to perform the operation.
- (4) Surgical success rate, intraoperative blood loss, operative time, and installation time are recorded, as well as whether adjacent organs and blood vessels are injured due to the malfunction of the test system. The breakage rate of gallbladders is calculated. Surgeons need to fill the satisfaction questionnaire after the surgery.
- (5) Subjects take a test in 24 ± 2 hours after surgery using visual analogue scale (VAS) to evaluate the pain score. Postoperative blood routine examination, liver and kidney function, and electrolyte examination are performed. Time to first flatus, postoperative complications and hospital stay are recorded. Postoperative combined medications are also recorded. Adverse events and severe adverse events are assessed separately in 30 ± 5 days after surgery.
- (6) After the follow-ups of all subjects, the data will be arranged for statistical analysis. Ultimately the data of the two groups will be compared, so as to prove whether the experimental product developed by WEGO Surgical Robot Co., Ltd is non-inferior to the control group.

6. Arms and Interventions

- (1) Experimental group: MicroHand S endoscopic instrument control system
Using the MicroHand S endoscopic instrument control system to treat gallstone or cholecystitis in minimal invasive surgery.

(2) Control group: da Vinci endoscopic instrument control system

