7.6 Number of subjects required

In this clinical trial, 168 patients are enrolled, including 84 in the experimental group and 84 in the control group.

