8.1 Primary outcome measure: surgical success rate

The surgical success rate is defined as the proportion of successfully operative subjects in the experimental group or the control group.

Surgery conversion in this study means a robotic surgery has to be converted to a

laparoscopic surgery. Usually there are 3 kinds of reasons: active conversion, passive conversion and malfunction of the endoscopic instrument control system.

(1) Active conversion:

During the surgery, surgeons may encounter some situations that make them impossible to keep the operation going such as severe adhesion, anatomical variation or failing to expose the surgical site. Or when surgeons are dissociating the tissue, they have difficulties to find certain important vascular structure and to make a normal anatomy of the clearance. At this point, surgeons initiatively decide to convert to a laparoscopic surgery.

(2) Passive conversion:

During the surgery, some unexpected accidents happen and surgeons have to convert to laparoscopic surgery. Usually these accidents include injury of tissues and organs, unstoppable bleeding, and difficult suture using the surgical robot. Passive conversion is related to surgical techniques of the surgeons. With the experience accumulating and the operative skill improving of surgeons, the passive conversion rate will decrease significantly.

(3) Malfunction of the endoscopic instrument control system:

Serious malfunction of the test product may occur during the surgery (such as strong interference between the console and the operative part, the operative arm dysfunction and can't be repaired by resetting, surgical instrument can't loosen the tissue, etc.) The operation is unable to continue, so surgeons have to convert to laparoscopic surgery. Usually the malfunction is caused by unreasonable design, unqualified instruments or inappropriate operation of the product arms. It indicates the deficiency of the test product.

Notes:

1) Surgical success is defined as the successful completion of all surgical operations through the experimental products or the control products.

2) Surgical failure is defined as the unaccomplishable surgical operations using the experimental or control products as planned. The reason includes passive conversion and malfunction of the products. Noticeably, active conversion does not mean a surgical failure.

8.2 Secondary outcome measures:

(1) The breakage rate of gallbladder:

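### The injury indicator counts only malfunction-caused injury, while section 1 aims at product-related injury and section 2 at injury of any cause, so a zero would not mean that no injury occurred

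*Protocol*

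**What the plan says.** The aim appears twice in the protocol, with different scope. Section 1 (Study purpose) undertakes "to observe the incidence of organ and vascular injury related to the test product". Section 2 (Content) says that the robotic systems are used "in both groups to evaluate the primary and secondary outcome measures and to observe the incidence of organ and vascular injury", and sets no condition on cause.

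The operative text is narrower. Among the items recorded during the operation, section 5(4) lists "whether adjacent organs and blood vessels are injured due to the malfunction of the test system". Section 9.1(1) opens with a general heading on organ and vascular injury, then lists two items. The first is "Any damage to the adjacent organs (liver, spleen and intestine) due to the malfunction of the products". The second is vessel injury that was caused by product malfunction and also led to massive bleeding. No threshold for massive bleeding is given.

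Section 8.1(2) describes the accidents behind passive conversion: "Usually these accidents include injury of tissues and organs, unstoppable bleeding, and difficult suture using the surgical robot". It adds: "Passive conversion is related to surgical techniques of the surgeons". Malfunction is a separate category, in 8.1(3).

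On size, section 7.6 states: "168 patients are enrolled, including 84 in the experimental group and 84 in the control group".

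**The concern.** An indicator headed as the incidence of organ and vascular injury will be read as the answer to the aim in section 2. As listed, it answers a smaller question: how often did a malfunctioning device injure the patient? An organ or vessel injured while the device works properly is outside the two listed items. It can still be injury of the kind that section 2 aims to observe. It can also be product-related in the sense of section 1, since a working device may contribute to an injury.

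At stake is the reading of a safety result. A report of no organ or vascular injury in 84 patients could be taken as an all-cause finding when the definition behind it cannot support one. The protocol itself foresees injuries of the omitted kind.

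**Working it through.** The protocol states no figure for this indicator, so there is none to reproduce. The check compares the passages, and one calculation shows what a zero count would mean.

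**Step 1: scope of each passage**

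- Section 1: injury related to the test product. Malfunction is not required.
- Section 2: injury in both groups. No cause is required.
- Section 5(4): malfunction required.
- Section 9.1(1), organs: malfunction required.
- Section 9.1(1), vessels: malfunction and massive bleeding both required.

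The recording rule and the indicator agree with each other on malfunction. Both are narrower than either statement of the aim, and the gap is widest against section 2.

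**Step 2: does the protocol expect injury without malfunction?** Yes. Section 8.1(2) names organ injury and bleeding, links passive conversion to technique, and keeps malfunction apart. The line is not perfectly clean. Section 8.1(3) counts improper handling of the arms among the causes of malfunction, and 9.1(3) counts instrument failure or damage as malfunction. Some operator-related injuries could therefore enter 9.1(1).

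**Step 3: where else could an injury without malfunction appear?**

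- Primary outcome (8.1): only if it forces passive conversion, and then as a surgical failure, not as an injury. Note 2 in 8.1 says that active conversion is not a failure, so conversion as such does not bring an injury into the primary outcome.
- CCI (8.2(2)): this takes events after the surgical intervention, so the injury needs a postoperative consequence.
- Adverse events (9.1(2)): the window opens at the end of the operation and closes at discharge. Again a postoperative consequence is needed.
- Intraoperative bleeding (8.2(4)): this gives a volume and does not identify an injury.
- Thirty-day assessment (5(5)): "Adverse events and severe adverse events are assessed separately in 30 ± 5 days after surgery". No limit on onset is set, so an intraoperative injury might be captured, but the text does not say so.

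None of these yields an incidence of organ and vascular injury from any cause. An injury repaired during the operation, without passive conversion and without postoperative consequence, is not clearly assigned to any named event indicator.

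**Step 4: what a zero would show.** Input: n = 84 per arm (section 7.6). With no events, the exact (Clopper-Pearson) two-sided 95% upper bound is 1 − 0.025^(1/n):

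1 − 0.025^(1/84) = 1 − 0.9570 = 0.0430, or 4.3%.

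The bound applies to the events that 9.1(1) lists, which are malfunction-caused injuries. It sets no limit on injury from other causes.

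**The case against.** The strongest case for the plan has five parts.

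- **The formal aim is device-specific.** Section 1 limits it to the test product, and malfunction is one way to make that operational. Section 2 is an overview. This narrows the gap but does not close it: product-related is still wider than malfunction-caused, and section 2 does state the broader aim.
- **The list may be open.** The heading of 9.1(1) introduces its items with a word that need not mean a complete list. That is true. But both listed items require malfunction, and so does the only recording instruction for injury, so no other injury is specified for the count.
- **Other measures cover much of the gap.** They do, as traced above, but not as an injury incidence.
- **The harm needs a misreading.** The malfunction condition is stated openly, and nothing in the protocol equates a zero with no injury. This stands, and it is one reason to rate the point low.
- **The aim could be narrowed instead.** This would also remove the contradiction, but it would leave unanswered the question that section 2 sets.

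Stronger readings are tempting but not supported. A reader might infer that technique-related injuries go unrecorded altogether. No CRF is shown, so what is actually collected cannot be judged. A reader might also infer from the reference to the test system in 5(4) that injuries are counted in one arm only. Section 2 names both groups and 9.1 speaks of the products, so this is better read as loose wording.

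**Conclusion.** The point holds as a mismatch between the stated aims and the indicator as worded. Followed as written, 9.1(1) would undercount any organ and vascular injury that arises without malfunction, and no other named indicator supplies the any-cause incidence. The conclusion takes the two items in 9.1(1) as defining the count, which 5(4) supports but does not prove.

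The number of injuries affected cannot be derived. The protocol gives neither an injury rate nor the share due to malfunction, so no claim is made on frequency. The only firm figure is the 4.3% upper bound, and it is limited to malfunction-caused injury.

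The definition of the primary outcome, its comparison between arms and the sample size are not touched. The severity is minor, and the change is a cheap improvement.

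**What to change.** In 5(4) and 9.1(1), record any intraoperative organ, bile-duct or vascular injury from any cause, identically in both arms. Use the window that 8.2(4) already uses for blood loss, from the start of the operation to the end of suture. Report malfunction-caused injuries and injuries with massive bleeding as subsets, so that the device-specific indicator is kept. The bile duct should be named because it is absent from the organs in 9.1(1), although 10.2(5) tells surgeons to identify the common bile and hepatic ducts.

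In 5(4), refer to the assigned product in place of the test system. Align sections 1 and 2 with the revised 9.1(1).

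The cost is wording in four places (sections 1, 2, 5(4) and 9.1(1)) and at most one extra CRF item per operation, which may already exist. The reported injury rate may be higher in both arms. Sample size and primary outcome stay as they are.

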The breakage rate of gallbladder is defined as the proportion of the subjects in the experimental group or the control group with specimen breakage.

(2) Comprehensive Complication Index (CCI)

CCI is calculated using online tools provided by <http://cci.assessurgery.com>. Based on the Clavien-Dindo complications grade system (appendix.1), all complications and adverse events after surgical intervention are taken into consideration. The overall incidence is measured on a scale ranging from 0 (no complication) to 100 (death).

(3) Operative time (min)

The length of time from the beginning of the operation after the robot installation to the end of the suture of the incision.

(4) Intraoperative bleeding (L)

The total bleeding volume from the beginning of the operation to the end of the suture of the incision. It can be calculated by measuring the blood volume in the vacuum suction device and weighing the gauze after using them to wipe the bleeding.

(5) Postoperative pain

Postoperative pain is assessed by visual analogue scale (VAS) 24-26 hours after the operation, ranging from 0 (no pain) to 10 (maximum pain).

(6) Time to first flatus (h)

The time from the end of the operation to the subject's first flatus after surgery.

(7) Surgeon's satisfaction

After the operation, surgeons fill a questionnaire to score the flexibility, intuition and stability of the products, as well as their sense of delay and fatigue when using the products. Each question in the score ranges from 1 to 5 points and the total score is 100.

(8) Installation time (min)

The time from the power-on of the products to the end of the connection between trocars and the operative arms.

(9) Hospital stay (days)

The total hospital days of subjects from admission to discharge.

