10.2 Standard operating procedures

- (1) Examining the console: appearance inspection, instrument performance, screen display and technical index.
- (2) Examining the operative arms: appearance inspection, movements, instrument performance, and technical index.
- (3) Connecting the endoscopic instrument control system and preparing the initialization of the system for a few seconds.
- (4) Starting the operation: anesthesia, position adjustment, pneumoperitoneum, setting trocars, and 3D laparoscopic light source.
- (5) Brief procedures of the operation:
 - 1) The surgeons control the operative arms to grab the neck of the gallbladder or Hartmann's fossa with the bipolar electric knife and pull it to the upper right.
 - 2) The surgeons use the electric hook to dissociate the serosal membrane of gallbladder tube, make blunt dissection of gallbladder tube and gallbladder artery, and pay attention to distinguish common bile duct and common hepatic duct.
 - 3) The surgeons use hemo-lok clips to clamp the tube as close as possible to the neck of the gallbladder, and cut with surgical scissor between two hemo-lok clips.
 - 4) The surgeons clamp the neck of the gallbladder and pull upward. Simultaneously, we use ultrasonic knife to carefully detach along the gallbladder wall. The assistant should pull gently to hold the tension between the gallbladder and liver, which makes it easier to detach.
 - 5) After fully dissociation of the gallbladder, the surgeons take it out of the abdominal cavity through the 12mm trocar. Then we check if there is any bleeding or leakage before withdrawing orderly.
 - 6) The surgeons suture the surface wounds and turn down the products.

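### On its natural reading, the organ-injury safety indicator leaves out malfunction-caused injury to the common bile duct or common hepatic duct

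*Protocol*

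**What the plan says.** The study purpose (protocol section 1) sets out "to observe the incidence of organ and vascular injury related to the test product" beside the non-inferiority comparison, and section 2 repeats that aim.

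Section 9.1(1) defines the indicator. Its lead-in is "The incidence of organ and vascular injury events which include the following", and two items follow:

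- Item 1): "Any damage to the adjacent organs (liver, spleen and intestine) due to the malfunction of the products".
- Item 2): "The blood vessel injury caused by the malfunction of the products during the operation resulting in massive bleeding".

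The recording step for the operation, section 5(4), asks "whether adjacent organs and blood vessels are injured due to the malfunction of the test system". It gives no list of organs.

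The operative steps in 10.2(5) 2) tell the surgeon, while freeing the cystic duct and artery, to "pay attention to distinguish common bile duct and common hepatic duct".

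**The concern.** The operation described in 10.2 is removal of the gallbladder. The common bile duct and common hepatic duct are the only structures that its steps tell the surgeon to distinguish, so the protocol recognises them as lying close to the dissection. They do not appear among the organs in the injury indicator.

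At stake is the meaning of a low or zero count. If a malfunction in either arm led to a duct injury, the organ and vascular injury incidence could still be reported as zero under the definition as written. Two sites could also code the same event differently, one reading the bracket as complete and the other reading it as examples.

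**Working it through.** The protocol states no figure to reproduce here, so the check is mainly a reading of the definitions.

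**Step 1: does a malfunction-caused duct injury enter 9.1(1)?**

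| Item | Structures | Further condition | Duct injury counted? |
|---|---|---|---|
| 9.1(1) 1) | liver, spleen, intestine | caused by malfunction | No: the structure is not listed |
| 9.1(1) 2) | blood vessels | caused by malfunction, with massive bleeding | No: a bile duct is not a blood vessel |

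A duct cannot easily be read as part of the liver. The imaging list in 10.1(5) names liver and bile as separate items.

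**Step 2: is the list closed?** The bracket follows a definite phrase, the adjacent organs, and carries neither *such as* nor *etc.* The protocol uses those words where a list is open, for example in 7.2(7) and in the malfunction paragraph of 8.1. Pointing the other way, the lead-in to 9.1(1) uses *include*. That verb does not settle the matter: note 2) of 8.1 uses it for the two reasons for surgical failure and then rules out active conversion, so there it introduces a complete list. The closed reading is the natural one, and the open reading is possible.

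**Step 3: is the injury counted elsewhere?**

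- *Primary outcome (8.1).* Tissue or organ injury is given as a reason for passive conversion, which is a failure. It counts only if conversion is forced. A duct injury dealt with robotically remains a success.
- *Adverse events (9.1(2)).* The indicator is "The incidence of adverse events from the end of the operation to discharge". An event during the operation precedes this window, although its consequences may fall inside it.
- *CCI (8.2(2)).* Here "all complications and adverse events after surgical intervention are taken into consideration", but they are merged into one score from 0 to 100.
- *Adverse events at 30 ± 5 days (5(5)).* These may show later consequences.
- *Malfunction incidence (9.1(3)).* This counts the device event, not the injury.

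Several of these could reveal the injury. None gives a count, by arm, of ducts injured through malfunction.

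**Step 4: size.** Input: 84 subjects per arm (section 7.6), assuming all are analysed.

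- One omitted malfunction-caused duct injury: 1/84 = 0.0119, or 1.2 percentage points of that arm's incidence.
- Two omitted: 2/84 = 0.0238, or 2.4 percentage points.

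The documents give no rate of malfunction-caused duct injury. Taking 0 to 2 such events per arm as an assumption, the understatement runs from 0 to 2.4 points. The point rests on the definition and not on this range.

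**The case against.** The strongest reply is that the gap is narrow.

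- *The malfunction condition does most of the excluding.* Both items of 9.1(1), and 5(4), require a malfunction. A reader might infer that every duct injury in the trial is lost because of the organ list. The text does not support that: a duct injury without a malfunction is excluded by the causal condition whichever organs are named. Only the malfunction-caused subset is lost through the list. This stands, and it limits the size.
- *The warning in 10.2(5) 2) concerns identifying anatomy, not device failure.* This also stands. It shows that the protocol treats the ducts as relevant to the operation, and does not show that malfunction-caused duct injury is expected.
- *The list may be open, and 5(4) has no list.* This stands in part. Recording under 5(4) is not confined to three organs, and the case report form is not shown, so it cannot be said that sites have nowhere to record the event. But 5(4) uses the same term, adjacent organs, and the only place that spells the term out omits the ducts.
- *A serious duct injury would hardly go unseen.* That is fair, given conversion, adverse events, the CCI, the malfunction count and the liver function tests in 9.1(5). Being visible somewhere is still different from being counted in the indicator that the study purpose names.

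**Conclusion.** The point holds as a defect of definition. On the natural reading, 9.1(1) does not count a malfunction-caused injury to the common bile duct or common hepatic duct; at best it is unclear whether it does. Each such event left out lowers an arm's reported incidence by 1.2 percentage points, with 84 subjects analysed per arm. The number of such events to expect is unknown from the documents and may be zero. No sample size or power figure is affected.

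A reader might go further and infer that the trial could establish safety on this indicator alone. The protocol does not say so: 9.1 lists five groups of safety indicators and sets no test or threshold on the first. Nor do the documents support an argument that the spleen should not be on the list, since 9.1 itself calls it adjacent, or a claim about how common or how characteristic duct injury is in this operation.

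**What to change.** In 9.1(1) 1), add the extrahepatic bile ducts (common bile duct and common hepatic duct) to the listed structures. In 5(4), make clear that adjacent organs includes them, so that the event is recorded at the operation and need not be reconstructed at analysis.

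This is a change to a measurement definition. It needs a short wording change in two places and adds no procedure for subjects. The malfunction condition stays as it is, so duct injuries without a malfunction remain outside the indicator. The downside is that the reported injury incidence may be slightly less favourable.

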7.5 The expected duration time of each subject

Each subject is observed up to 30 days after surgery, and efficacy and safety are evaluated at the end of the follow-up. So the expected duration of each subjects is 33 days. The additional 3 days are used for preoperative examination.

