7.7 Drop-outs and removal of the subjects

All subjects who sign the informed consent form and participate in the study, whenever they withdraw from the study for any reason, as long as they do not complete the observation period specified in the protocol, they are shedding cases. Usually in these situations:

- (1) The subject or his/her legal guardian requests to withdraw from the clinical trial.
- (2) Adverse events (AE), severe adverse events (SAE), or any device defects that prevent subjects from continuing to participate in the study.
- (3) The researchers consider it medically necessary for the subjects to terminate the study.
- (4) Other reasons for subjects to suspend the study.

When the subject drops out, the researcher should take various methods, such as paying a visit, making a follow-up appointment, phone call, letter, etc., to contact the subject as far as possible and ask the reason. Any drop-out due to adverse events should be recorded in the CRF form and notified to the sponsor, regardless of whether there is a causal relationship with the test product or not. All subjects enrolled in the study should retain various original data and documents, both for retention and for intentional analysis (ITT Analysis).

All subjects meeting the following criteria should be removed:

- (1) Those found to violate the inclusion criteria or meet the exclusion criteria during the trial.
- (2) Withdrawing the informed consent.
- (3) The informed consent form is not signed or there is no informed consent process.
- (4) Failing to obtain observation data.

Case removal is one of the key indicators to determine the endpoint data set of clinical trials. If there is a condition that affects the treatment or safety evaluation of the case, such as unavailable observational data, the case should be considered as not included in the analysis set. It must be decided after discussion between the principal investigator, the data manager, the statistical analyst and the sponsor.

8. Efficacy evaluation

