9.2 Indicators measurement methods

- (1) Vital signs: Twice a day before surgery, twice at the beginning and end of the operation, and twice at 3-5 days after the operation. Six times in total.
- (2) Laboratory examination: once before the operation and once within 3~5 days after the operation. At least twice in total.

10. Procedures

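### The only general adverse-event incidence in 9.1 stops at discharge, although adverse events are assessed at 30 ± 5 days and safety is evaluated after 30-day follow-up

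*Protocol*

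**What the plan says.** Four places in the protocol bear on when AEs are counted.

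- **9.1(2), safety indicators:** "The incidence of adverse events from the end of the operation to discharge". This is the only general AE incidence in the list. No SAE incidence is named.
- **5(5), study methods:** "Adverse events and severe adverse events are assessed separately in 30 ± 5 days after surgery".
- **7.5, subject duration:** "Each subject is observed up to 30 days after surgery, and efficacy and safety are evaluated at the end of the follow-up".
- **8.2(2), CCI:** "all complications and adverse events after surgical intervention are taken into consideration". The result is a score from 0 to 100, and no end date is given.

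The other indicators in 9.1 are organ and vessel injury due to malfunction (1), product malfunction (3), vital signs (4) and laboratory tests (5). No passage says how the window in 9.1(2) relates to the assessment in 5(5) or the evaluation in 7.5.

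**The concern.** Section 1 makes safety a purpose of the trial alongside efficacy. The trial follows every subject for about a month and records AEs and SAEs at the end, yet the general AE rate that it defines covers the hospital stay only. Three things follow.

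1. A general AE or SAE that starts after discharge is collected but counted in no general incidence. The same records could therefore give two different AE rates, one in-hospital and one to day 30, and only the first is a named indicator.
2. Discharge is a different day for each subject. If postoperative stay differs between the arms, so does the time in which an AE can be counted.
3. The window opens when the operation is over, so an event during the operation falls outside it.

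**Working it through.** **Step 1. The protocol's own figure.** Section 7.5 gives 30 days of follow-up and 3 days of preoperative examination: 30 + 3 = 33 days, as stated in 7.4 and 7.5. The planned subject duration therefore rests on follow-up to day 30, not to discharge.

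**Step 2. The windows side by side.**

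| Place | Opens | Closes |
|---|---|---|
| 9.1(2) AE incidence | end of operation | discharge, no fixed day |
| 5(5) AE/SAE assessment | not stated | day 30 − 5 = 25 to day 30 + 5 = 35 |
| 7.5 safety evaluation | not stated | day 30 |
| 8.2(2) CCI | after surgery | not stated (7.5 may imply day 30) |

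**Step 3. Where a post-discharge AE can appear.**

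- 9.1(1)1), organ damage due to malfunction, has no end date, so such an injury recognised after discharge can still count.
- 9.1(1)2), vessel injury, is confined to the operation.
- 9.1(3) counts device malfunctions, not patient events.
- 9.1(4) and 9.1(5) report vital signs and laboratory results. The postoperative laboratory check is timed in 9.2 as "once before the operation and once within 3~5 days after the operation", without reference to discharge.
- The CCI may take in later events, but as a severity-weighted score.

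None of these gives the proportion of subjects with any AE, or with an SAE, by day 30.

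**Step 4. Where an intraoperative event can appear.** 9.1(1) takes malfunction-related injury to the listed organs and vessels. 8.2(1) reports gallbladder breakage directly, and 8.2(4) reports blood loss. Passive conversion in 8.1 may reflect tissue injury or bleeding. An intraoperative AE outside these has no indicator of its own, and none of them enters 9.1(2).

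**Step 5. Share of follow-up time outside 9.1(2).** The protocol gives no expected discharge day, so discharge on postoperative day d is an assumption. Days outside = 30 − d; share = (30 − d)/30.

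| Assumed d | Days outside | Share of 30 days |
|---|---|---|
| 1 | 29 | 96.7% |
| 3 | 27 | 90.0% |
| 5 | 25 | 83.3% |
| 7 | 23 | 76.7% |

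These are shares of days. The protocol gives no AE rate and no timing of AEs, so they cannot be turned into shares of events.

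**Step 6. Difference between arms.** Under 9.1(2), counted time equals d. Purely as an illustration, discharge on day 3 in one arm and day 5 in the other gives 3 against 5 days; a window fixed at day 30 gives 30 in both. The protocol states no expected difference in stay. Hospital stay in 8.2(9) runs from admission, so it does not measure postoperative time directly.

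**The case against.** The strongest reply is that nothing here is contradictory. AEs can be collected to day 30 and an in-hospital rate reported. 9.1(2) does not call itself the only AE summary, and tabulation of later events may be left to the SAP. The first part stands: there is no conflict in conduct and no loss of data. The second part stands only in part, because the protocol does not leave the window open. It fixes it, and an SAP that used 30 days for this indicator would depart from the protocol.

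Several stronger readings are tempting, and the documents do not support them.

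- *Post-discharge events enter no incidence in 9.1 at all.* Too broad: 9.1(1)1) has no end date.
- *A laboratory abnormality found on days 3 to 5 is lost once the subject has gone home.* It is still reported under 9.1(5), and vital signs under 9.1(4). Only its counting as an AE under 9.1(2) depends on discharge. No passage shows that subjects leave before that check.
- *Intraoperative harm is seen only indirectly, or every malfunction-related AE is already covered.* Neither holds. Gallbladder breakage is reported directly in 8.2(1), while 9.1(1) is limited to listed injuries and 9.1(3) counts device faults.
- *The CCI settles the matter.* Section 8.2(2) does describe its result as an overall incidence, but a 0-to-100 burden score cannot give the proportion of subjects with an AE.

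It is also fair to say that 9.1(2) is not the primary outcome, and that the specific safety aim in section 1 is "to observe the incidence of organ and vascular injury related to the test product". The non-inferiority conclusion on surgical success does not depend on this point.

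**Conclusion.** The point holds as an unreconciled endpoint definition that should be corrected. Followed as written, 9.1(2) omits general AEs and SAEs that the trial already collects after discharge, ends on a day that varies by subject, and excludes the operation.

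The size and direction of the effect on the AE rate, or on the difference between arms, cannot be derived, because the protocol gives neither AE rates nor discharge days. Only time can be bounded: 97% to 77% of the 30 days lie outside the window for assumed discharge on days 1 to 7. A reader might take this as the share of AEs missed; nothing in the protocol supports that, since AEs need not be spread evenly over the month. A reader might also infer a bias for or against the test device. That would need a difference in postoperative stay, and none is stated.

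**What to change.** Reconcile 9.1(2) with 5(5) and 7.5 as follows.

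- Define AE incidence and SAE incidence from the start of the operation to postoperative day 30, as captured at the existing 30 ± 5 day assessment.
- State the counting rule for that tolerance. Events after day 30 are not counted, and subjects assessed on days 25 to 29 are counted to their assessment. No extra contact is needed, so the tolerance in 5(5) is kept.
- Keep the present 9.1(2) incidence as a named in-hospital sub-period.
- List intraoperative events separately.
- State the same 30-day end for the CCI in 8.2(2) and leave its start unchanged.

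The cost is wording, with no new visit. The downsides are slightly more reporting, a possibly higher reported AE rate, and up to 30 − 25 = 5 days less observation for subjects assessed early, so the window is nearly but not exactly equal for all.
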